11.4. Procedures for Handling Missing, Unused, and Spurious Data

All available efficacy and safety data will be included in the data listings and tabulations. No imputation of values for missing data will be performed.

11.5. General Methodology

Summary of tabulations will be presented by treatment group displaying the number of observations, mean, standard deviation, median, minimum, and maximum for continuous variables, and the number and percent per category for categorical data.

11.6. Baseline Comparisons

Demographic and baseline characteristics will be summarized by treatment group.

11.7. Efficacy Analysis

The Phase II portion of the study will follow a Simon two-stage design to compare a null ORR of 15% with an alternative ORR of 40% with 90% power and a one-sided type I error of 5%. The total sample size will be 29 evaluable patients. Thirteen patients will be enrolled in the first stage, with at least three responses required to proceed to the second stage. Eight responses among 29 patients are required for PLX3397 to be considered promising. See Section 11.10 for discussion of interim analysis.

Object tumor response to treatment will be evaluated using investigator-determined RECIST v1.1 ([ATTACHMENT 3](#)). PFS, OS and duration of response will be evaluated as secondary efficacy endpoints. PFS will be calculated for each patient as the number of days from study

enrollment to the date of the first documented disease progression or date of death from any cause, whichever occurs first. Overall survival is defined as the time from study enrollment to death from any cause, censoring at the date of last contact or the end of the study. Duration of response (DoR) is defined as the time from the first documentation of objective tumor response (CR or PR) that is subsequently confirmed to the first documentation of disease progression or to death due to any cause, whichever occurs first. DoR will only be calculated for the subgroup of patients with a confirmed objective tumor response. Sponsor may request imaging data for the confirmation of the tumor response.

The Kaplan-Meier method will be used to estimate the median PFS, OS and DoR.

11.8. Pharmacokinetics/Pharmacodynamics/Biomarkers

11.8.1. Pharmacokinetic Analysis

The PK profile of plasma PLX3397 will be analyzed by measurement of area under the plasma concentration-time curve (AUC_{0-6}), peak concentration (C_{max}), and time of maximum observed concentration (T_{max}). To evaluate plasma exposure accumulation after repeated dosing, accumulation ratios of Day 15 to Day 1 for AUC_{0-6} and C_{max} (R_{obs} and RC_{max} , respectively) will be determined.

11.8.2. Pharmacodynamic Analysis

No formal statistical analysis of PD endpoints will be performed. PD data from each assay will be listed, and possible relationships between clinical response and PD variables will be explored. Any biological activity will be described.

11.8.3. Tissue Evaluation

At least 10 unstained FFPE slides of 5 μ m thickness from the archival tissue should be submitted on all participants in the study. The archival tissue may be from the original diagnosis, or from a biopsy obtained after a previous therapy. Slides should be air-dried (NOT baked) onto positively charged slides. A representative paraffin block can also be provided, which will be returned to the study site after sectioning. For patients undergoing paired fresh biopsy, at least 10 sections are also requested, and at least 20 unstained FFPE slides of 5 μ m thickness from the fresh tissue should be submitted (Phase I and first 13 patients enrolled in Phase II).

Exploratory tissue studies will include IHC for KIT, pERK, Ki67. Tissue may also be used for KIT or other oncogene mutation sequencing confirmation. Other exploratory evaluations may include assessment of the tumor microenvironment by IHC or other methods for immune cell expression/number (e.g., PD-1). Exploratory blood studies will measure CSF-1 and ctDNA (Phase II portion in Korea only). Planned biomarkers are listed in [ATTACHMENT 1](#).

11.9. Safety Analysis

Safety variables to be assessed will include AEs, laboratory test results (hematology, serum chemistry, and urinalysis), ECG, weight, and vital signs.

Adverse event terms recorded on the eCRFs will be mapped to preferred terms using the Medical Dictionary for Drug Regulatory Activities (MedDRA[®]) version 17.0 or later. All AEs will be summarized according to the system organ class and preferred term within the organ class. Adverse events will be tallied for overall frequency (number and percentage of patients), worst reported severity, and relationship to study drug for each preferred term per patient. SAEs will be similarly summarized. Listings of deaths, SAEs, and AEs leading to early termination of study treatment or premature withdrawal from study will also be provided.

Laboratory variables will be examined using mean change in value from baseline to scheduled time points. Laboratory values will also be categorized according to their CTCAE (version 4.03) toxicity grade and tabulated by worst on-study toxicity grade. The baseline value of a variable is defined as the last value obtained on or before the date and time of the first PLX3397 dose.

ECG, weight, and vital signs will also be summarized by changes from baseline to scheduled time points using descriptive statistics. Changes in QTcF will also be evaluated for the proportion of patients with absolute values >500 msec and change from baseline >60 msec.

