
Inclusion/ Exclusion Criteria:
	
To be eligible for enrollment, patient must meet all inclusion and exclusion criteria.
 
Inclusion Criteria:
 
 1. Age ≥18 years 2. Unresectable stage III or stage IV melanoma which is histologically confirmed at the treating institution with KIT mutation(s) not known to be resistant to PLX3397 (see Table 9-1). Note: Patients with KIT exon 8, 9, 11, 13, and 14 mutations are the most likely to be sensitive to PLX3397. Patients with KIT exon 17 or 18 mutations D816V, Y823D, and A829P should not be enrolled as they are not sensitive to PLX3397. Other KIT exon 17 or 18 mutations may be sensitive to PLX3397 and should be enrolled. 3. No limit on prior systemic therapies for melanoma. Patients who have not received prior therapy are eligible if they have a potentially sensitive KIT mutation. 4. Presence of measurable lesions by RECIST v1.1 5. ECOG performance status 0, 1, or 2 6. Life expectancy ≥3 months in the judgment of the investigator 7. Adequate organ and bone marrow function 
 a. Absolute neutrophil count (ANC) ≥1.5 X 10⁹/L, Hgb ≥10 g/dL, platelet count ≥100 X 10⁹/L b. AST/ALT ≤2.5 X upper limit of normal (ULN) or <5 X ULN in the presence of liver metastases, total bilirubin ≤1.5 ULN (unless due to Gilbert’s Syndrome, in which case it must be ≤2.5 mg/dL), albumin ≥3.0 g/dL c. Serum creatinine ≤1.5 X ULN or calculated creatinine clearance (CrCl) >60 mL/min using the Cockcroft-Gault formula 
Patients may be transfused or receive granulocyte-colony stimulating factor (G-CSF) or growth factors.
 8. Women of child-bearing potential must have a negative serum pregnancy test at Screening and must agree to use an effective form of contraception from the time of the negative pregnancy test up to 3 months after the last dose of study drug. Effective forms of contraception include abstinence, hormonal contraceptive (injectable or implantable) in conjunction with a barrier method, or a double barrier method. Women of non-child-bearing potential must have been postmenopausal for ≥1 year or surgically sterile. 9. Fertile men must agree to use an effective method of birth control during the study and for up to 3 months after the last dose of study drug. 10. Willingness and ability to provide written informed consent prior to any study-related procedures and to comply with all study requirements 
Exclusion Criteria:
 
 1. Prior treatment with a KIT inhibitor for melanoma 2. Known presence of NRAS or BRAF mutation

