6.1. Inclusion Criteria

Each patient must meet all of the following inclusion criteria to be enrolled in the study to treatment:

1. Age ≥ 18 years
2. Unresectable stage III or stage IV melanoma which is histologically confirmed at the treating institution with KIT mutation(s) not known to be resistant to PLX3397.

Note: Patients with KIT exon 8, 9, 11, 13, and 14 mutations are the most likely to be sensitive to PLX3397. Patients with KIT exon 17 or 18 mutations D816V, Y823D, and A829P should not be enrolled as they are not sensitive to PLX3397. Other KIT exon 17 or 18 mutations may be sensitive to PLX3397 and should be enrolled.

3. No limit on prior systemic therapies for melanoma. Patients who have not received prior therapy are eligible if they have a potentially sensitive KIT mutation.
4. Presence of measurable lesions by RECIST v1.1
5. Eastern cooperative oncology group (ECOG) performance status 0, 1, or 2
6. Life expectancy ≥ 3 months in the judgment of the investigator
7. Adequate organ and bone marrow function
 - a. Absolute neutrophil count (ANC) $\geq 1.5 \times 10^9/L$, Hgb ≥ 10 g/dL, platelet count $\geq 100 \times 10^9/L$
 - b. AST/ALT $\leq 2.5 \times$ upper limit of normal (ULN) or $< 5 \times$ ULN in the presence of liver metastases, total bilirubin ≤ 1.5 ULN (unless due to Gilbert's Syndrome, in which case it must be ≤ 2.5 mg/dL), albumin ≥ 3.0 g/dL
 - c. Serum creatinine $\leq 1.5 \times$ ULN or calculated creatinine clearance (CrCl) > 60 mL/min using the Cockcroft-Gault formula

Patients may be transfused or receive granulocyte-colony stimulating factor (G-CSF) or growth factors.

8. Women of child-bearing potential must have a negative serum pregnancy test at Screening and must agree to use an effective form of contraception from the time of the negative pregnancy test up to 3 months after the last dose of study drug. Effective forms of contraception include abstinence, hormonal contraceptive (injectable or implantable) in conjunction with a barrier method, or a double barrier method. Women of non-child-bearing potential must have been postmenopausal for ≥ 1 year or surgically sterile.
9. Fertile men must agree to use an effective method of birth control during the study and for up to 3 months after the last dose of study drug.
10. Willingness and ability to provide written informed consent prior to any study-related procedures and to comply with all study requirements

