9.0 STUDY ASSESSMENT SCHEDULE

Event schedules are summarized in [Table 2-1](#) and [Table 2-2](#).

All patients must provide written informed consent. During the consent process, the person obtaining consent must inform the patient of all elements of the study. No protocol-specific procedures, including screening procedures, are to be performed until the patient has signed and dated an IRB/IEC-approved informed consent form. The study begins with the signing and dating of the informed consent form.

A patient will be considered enrolled in the study once all inclusion and exclusion criteria have been met, and the completed patient enrollment form has been submitted to the CRO, signed by the appropriate representative, and returned to the investigative site.

Screening procedures are to be performed within 28 days before C1D1 of study therapy.

The end of the study is defined as the date of the last dose of PLX3397 (see [Section 8.4](#) for reasons for discontinuation or withdrawal of a patient from the study).

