14.3. Monitoring of Adverse Events and Period of Observation

Adverse events, both serious and non-serious, and deaths will be recorded on the CRFs up to and including the last visit within 28 days after administration of the last dose of study drug and prior to the administration of any new anti-cancer therapy. All SAEs should be monitored until they are resolved or are clearly determined to be due to a patient's stable or chronic condition or inter-current illness(es). The AE collection period will begin when the patient signs informed consent.

Any SAE that occurs at any time after completion of the study and the designated follow-up period, which the investigator considers to be related to study drug, must be reported to the sponsor.

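### Section 11.9 does not separate pre-dose adverse events and entry laboratory abnormalities from on-treatment findings, which can inflate low-grade liver rates

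*Combined protocol and SAP*

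**What the plan says.** **Adverse events.** Section 14.3 states: "The AE collection period will begin when the patient signs informed consent". Screening may run for 28 days before the first dose. AE assessment is scheduled at Screening in Tables 2-1 and 2-2 and in Sections 9.1.1 and 9.2.1, and a tumor biopsy may fall in that window. Section 11.9 then says: "All AEs will be summarized according to the system organ class and preferred term within the organ class", tallied by frequency, worst severity and relationship. TEAE is in the abbreviation list but in no analysis rule. The AE definition in Section 14.1.1 points the other way: it speaks of events that are new, or have become worse, after drug was given.

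**Laboratory values.** Section 11.9 plans two summaries. The first is at group level: "Laboratory variables will be examined using mean change in value from baseline to scheduled time points". The second grades values by CTCAE, "tabulated by worst on-study toxicity grade". Baseline is defined: "The baseline value of a variable is defined as the last value obtained on or before the date and time of the first PLX3397 dose". For QTcF the same section also counts patients by size of change from baseline (more than 60 msec). Liver tests get no such patient-level rule.

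**Entry limits.** AST/ALT may be up to 2.5 x ULN, or "<5 X ULN in the presence of liver metastases, total bilirubin ≤1.5 ULN" (synopsis; repeated in Section 6.1).

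**Context.** Section 3.3 describes liver injury as an important and possibly fatal reaction to the drug. Section 5.1 records that six Pilot patients were enrolled and that the sponsor then decided to discontinue the study.

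**The concern.** With no control arm, a reader of the safety tables takes each incidence as a description of what happened on drug. Two of the planned tables do not support that reading. An event between consent and first dose, such as a complication of a screening biopsy, enters the AE table if 14.3 governs. An ALT that was raised at entry and never moved enters the worst-grade table, where it cannot be told apart from a normal ALT that rose on treatment to the same grade. Liver toxicity is where this matters most, because eligibility admits raised liver tests and the drug raises them. At stake is the accuracy of the low-grade liver rates and of AE incidence generally.

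**Working it through.** The plan states no figure on this point, so the check compares the sections and then sizes the effect.

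**1. AEs.** Take an event ten days before the first dose in a patient who is later dosed. Under 14.3 and the Screening assessments it is collected. Under 14.1.1 it is neither new nor worse since drug. Section 11.9 summarises all AEs and sets no onset date. The safety population in 11.3 removes patients who were never dosed; it does not remove pre-dose events of those who were.

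**2. Laboratory grades.** Let B be the baseline grade and W the worst on-study grade. The planned table uses W alone, so a patient with B = W > 0 looks the same as one with B = 0 and the same W. Section 11.9 does not define on-study. Section 9.0 says: "The study begins with the signing and dating of the informed consent form", which could let screening values in. Section 11.3, however, contrasts the screening baseline scan with on-study scans, which suggests that on-study means after baseline. An unchanged abnormality is counted on either reading, because the post-dose sample repeats it. A mean change cannot show which patients had B > 0.

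**3. How high an unchanged entry value can be.**
- AST/ALT below 5 x ULN can fall in the >3 to 5 x ULN band of Table 7-1, but not in the >5 to 10 or >10 x ULN bands.
- Total bilirubin at 1.5 x ULN or less is below 2 x ULN. It therefore reaches neither the upper total-bilirubin band of Table 7-1 nor the Hy's Law criterion in Section 13.1.
- Gilbert's syndrome is an exception, with a limit of 2.5 mg/dL. Since 2.5 / 2 = 1.25, such a patient could enter at 2 x ULN if the laboratory's ULN is 1.25 mg/dL or less. The protocol gives no ULN.
- Section 6.1 sets no entry limit for ALP, GGT or direct bilirubin, so this bound does not cover them.

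**4. Size per patient.** A patient counted in a row only because of a pre-dose finding adds 1/n:
- 1/6 = 16.7 percentage points (Pilot as enrolled)
- 1/12 = 8.3 points (largest planned Pilot)
- 1/32 = 3.1 points (Phase II as written)

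These are maxima. A patient who also has a qualifying post-dose finding belongs in the row anyway and adds nothing.

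**5. How likely.** The documents give no rate of liver abnormality at entry. Let q be the assumed share of patients who are in a row only because of an unchanged entry value, and assume that such a value receives a grade. The chance of at least one among n is 1 − (1 − q)^n. If a share t of the other patients has a new abnormality, the table shows q + (1 − q)t.

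| q (assumed) | At least 1 of 6 | At least 1 of 32 | Shown if t = 0 | Shown if t = 25% |
|---|---|---|---|---|
| 5% | 26% | 81% | 5% | 28.75% |
| 10% | 47% | 97% | 10% | 32.5% |
| 20% | 74% | >99% | 20% | 40% |
| 30% | 88% | >99% | 30% | 47.5% |

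For example, 1 − 0.90^6 = 0.469, and 0.10 + 0.90 × 0.25 = 0.325.

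**The case against.** The strongest reply has four parts.

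**The AE definition already excludes pre-dose events.** Section 14.1.1 refers to change since drug, and abnormal laboratory results become AEs when treatment-emergent and clinically significant. That probably shows the intent. It still conflicts with 14.3 and the Screening assessments, and it does not govern the grade table, which is built from laboratory values and not from recorded AEs.

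**Other safeguards exist.** AEs are tallied by relationship, and Section 14.2 treats an implausible time sequence as a ground for calling an event not related. All available safety data are listed (11.4). Combined aminotransferase and bilirubin elevations are reported within 24 hours with a narrative (13.1), and a committee adjudicates hepatic safety (15.12). All of this stands. A reader might infer that the incidence tables are the only safety evidence; the documents do not support that. These provisions do not correct the tables, and the grade table has no relationship column.

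**The error is towards caution.** This also stands. A reader might infer that serious liver signals are masked. They are not: worst grade still shows every severe value, and permitted AST/ALT and total bilirubin values fall short of the severe levels, Gilbert's syndrome aside. Nor does 11.9 lack a baseline altogether: it defines one and plans mean change from it. The gap lies in the AE and worst-grade tables.

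**Phase II was dropped and six patients can be read from listings.** This largely stands. A reader might apply an assumed 10–20% entry rate to 32 patients and conclude that 3 to 6 (3.2 to 6.4) would be miscounted. Under Section 5.1 the study was discontinued after the Pilot. That count also supposes that none of them worsens, whereas Section 3.1.2 reports transaminase increases in about half of patients at 600 mg/day or more. If half of those with raised entry values worsened, 1.6 to 3.2 would remain.

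**Conclusion.** The point holds for two tabulations. As written, 11.9 can count pre-dose AEs of dosed patients, and low-level liver abnormalities permitted at entry, as on-study findings. It inflates low-grade rates and does not conceal severe toxicity. In the six Pilot patients the size is at most 16.7 percentage points per affected patient per row. If 5–20% of patients have an unchanged entry abnormality, the chance that at least one of the six is affected is 26–74%. That range is an assumption, since the documents give no rate, and it treats patients as independent. The figures for 32 patients describe only the written plan. The low-level bound rests on the entry limits for AST/ALT and total bilirubin and does not extend to ALP, GGT or direct bilirubin. The correction is worth making because 11.9 already applies a patient-level change rule to QTcF and none to the liver tests.

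**What to change.** In Section 11.9:

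- Limit AE incidence tables to events with onset or worsening on or after the first dose, up to the end of the 14.3 collection window. List pre-dose AEs separately.
- Define on-study, for laboratory grading, as after the first dose.
- Replace the worst-grade table with shift tables of baseline grade by worst post-dose grade, at least for AST, ALT, ALP, GGT and bilirubin. Worst multiple of baseline is an optional addition.

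Reconcile Section 14.1.1 with 14.3, so that what is collected from consent and what is analysed as treatment-emergent are both explicit.

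The cost is table shells and a few sentences. Baseline and on-treatment values are already collected; no patients, visits or samples are added.

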11.10. Interim Analysis

The Phase II portion of the study will follow a Simon two-stage design to compare a null ORR of 15% with an alternative ORR of 40% with 90% power and a one-sided type I error of 5%. The total sample size will be 29 evaluable patients. Thirteen patients will be enrolled in the first stage before triggering an interim analysis. At least three responses are required to proceed to the second stage. Eight responses among 29 patients are required for PLX3397 to be considered promising.

12.0 ETHICAL CONSIDERATIONS

The study will be conducted in accordance with ethical principles founded in the Declaration of Helsinki. The IRB/IEC will review all appropriate study documentation in order to safeguard the rights, safety and well-being of the patients. The study will only be conducted at sites where IRB/IEC approval has been obtained. The protocol, Investigator Brochure, informed consent form, advertisements (if applicable), written information given to the patients (including diary cards), safety updates, annual progress reports, and any revisions to these documents will be provided to the IRB/IEC by the investigator or the sponsor, as allowable by local regulations.

13.0 EVENTS OF SPECIAL INTEREST

13.1 Combined Elevations of Aminotransferases and Bilirubin

Combined elevations of aminotransferases and bilirubin, either serious or nonserious and whether or not causally related, meeting the laboratory criteria of a potential Hy's Law case (ALT or AST $\geq 3 \times$ ULN with simultaneous total bilirubin $\geq 2 \times$ ULN) should always be reported to the Sponsor using a SAE reporting form along with the investigator's assessment of seriousness, causality, and a detailed narrative. These events should be reported within 24 h of the investigator's awareness of the events.

If the subject discontinues the study drug due to liver enzyme abnormalities, the subject will have additional clinical and laboratory evaluations in order to determine the cause and severity of the potential liver injury.

14.0 ADVERSE EVENTS

14.1 Definitions

14.1.1 Adverse Event Definition

An adverse event (AE) is any untoward medical occurrence in a patient administered a pharmaceutical product, which does not necessarily have a causal relationship with the treatment. An AE can be any unfavorable and unintended sign (e.g., including an abnormal laboratory finding), symptom, or disease temporally associated with the use of the study drug, whether or not it is considered to be study drug related. This includes any newly occurring event or previous condition that has increased in severity or frequency since the administration of study drug. Clear progression of the underlying cancer and hospitalizations due to the progression of cancer should not be reported as an AE, or a SAE. An AE includes, but is not limited to, the following:

- Any clinically significant worsening of a preexisting condition.
- An AE occurring from overdose (i.e., a dose higher than that indicated in the protocol) of a study drug, whether accidental or intentional.
- An AE occurring from abuse (e.g., use for nonclinical reasons) of a study drug.
- An AE that has been associated with the discontinuation of the use of a study drug.

Any treatment-emergent abnormal laboratory result which is clinically significant, i.e., meeting one or more of the following conditions, should be recorded as a single diagnosis on the adverse event page in the eCRF:

- Accompanied by clinical symptoms
- Leading to a change in study medication (e.g., dose modification, interruption or permanent discontinuation)

- Requiring a change in concomitant therapy (e.g., addition of, interruption of, discontinuation of, or any other change in a concomitant medication, therapy or treatment)

Adverse events will be graded in severity according to CTCAE v4.03 criteria.

